In order to enrol patients into this pilot study and to gain experience from International centres this study will be performed at 4 sites: the Royal Prince Alfred (RPA) Hospital Emergency Department, Sydney, Australia, Mount Sinai Hospital, Manhattan, NY, Maimonides Medical Center, Brooklyn, NY and NYC H+H/Lincoln Medical Centre, Bronx, New York, USA. The RPA Hospital is a Level 1 Trauma Centre with approximately 85,000 presentations and 240 intubations per year. Lincoln Medical Centre is a Level 1 Trauma Hospital with approximately 175,000 presentations and 450 intubations per year. Mount Sinai Hospital is a tertiary referral center whose ED sees approximately 125,000 patients per year with around 200 intubations. Maimonides Medical Center is a level 1 trauma center that treats about XXX and performs about XXX intubations per year.

Study Participants

All adult patients requiring emergent rapid sequence intubation (RSI) in the resuscitation bay will be included in the study. Patients that have a heavily soiled airway (i.e. secretions, vomitus, blood) as deemed by the physician requiring suction will be excluded.

Variables measured

The variables included in the study are shown on the Data collection sheet (Appendix 3) and will include the following:

- Patient details: Age, Gender, estimated weight
- Indication for RSI
- C-spine immobilisation and manual inline stabilisation
- Method of preoxygenation
- Method of apnoeic oxygenation, if performed
- Head up or supine position
- Oxygen saturation and ETO₂ prior to starting preoxygenation and at induction (completion of preoxygenation)
- Oxygen saturation and ETO₂ during procedure (at 10 second intervals starting with induction).
- Time of preoxygenation
- Induction medication and dose used
- Paralytic and dose used
- Induction time
- Endotracheal intubation time
- Method of intubation
- Number of attempts
- Cormack-Lehane grade of airway
- Use of cricoid or External laryngeal manipulation
- Continuous versus judicious suctioning

Intervention

The aim of this study is to investigate the effect of suctioning (a current technique used conventionally in RSI) on oxygenation levels during RSI. This being noted, there is no new intervention being applied to the patient.

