In order to investigate this, the current standard of care of suctioning will be used either by judicious means (i.e. in and out suction as needed) or continuous means (i.e. throughout the procedure, including laryngoscopy and tube placement) according to conventional practice at the discretion of the treating physician. For all patients involved in the study, there will be no new intervention applied. The impact of the use of suctioning, again which is standard of care and applied by convention, will be determined by measuring oxygen saturation as a primary outcome. All aspects of RSI will be at the discretion of the treating clinician, which is the current standard, including induction/relaxant medication, positioning of the patient, preoxygenation method, method of intubation and post-intubation sedation. At all institutions RSI is performed in a similar manner utilising an airway checklist (Appendix 1 and 2). However, there are no 'Standard Operating Procedures' for RSI in any ED and therefore intubation technique will vary depending on clinician preference and the clinical circumstances.

Once the decision to perform RSI has been made by the treating team, the patient will be enrolled into either a judicious or continuous suction group at random. In either case, suctioning will be applied to the patient as determined necessary by the clinician. Rapid sequence intubation will then be performed in the standard means by the treating provider.

Outcomes

Primary Outcome

The primary outcome of this study is the oxygen saturation achieved (SpO_2) at the time of tube placement (via confirmation with first ETCO_2 waveform) achieved during the intubation period.

Secondary Outcomes

The secondary outcomes measured include:

- Incidence of desaturation ($\text{SaO}_2 < 90\%$) or > 10 points from baseline during the intubation period
- Lowest O_2 saturations at any point during the intubation period
- The ETO_2 at induction and at ETT confirmation.
- Time from preoxygenation to endotracheal intubation
- Complications during RSI: bradycardia, tachycardia, hypotension, hypertension, oesophageal intubation, aspiration, airway or dental trauma, equipment or medication error
- Number of intubation attempts

Data Collection

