The data will be collected prospectively during the time of RSI by nursing and medical staff with the use of a data collection sheet (Appendix 3). Staff at RPA ED are familiar with the data collection sheets as prior studies in relation to RSI have been performed previously (Study number Re: X12- 0394). Similarly staff at Lincoln Medical centre and Mount Sinai perform routine data collection on all RSI's performed in the ED for quality improvement purposes. The staff at Maimonides and Mount Sinai will be trained in the procedure for collecting data with the use of the data collection sheets.

Patient risk

This study investigates the effect of providing suction during RSI on SpO₂ levels. This study will have no direct impact on patient care as it evaluates the use of a current accepted standard in the ED. This adds to clinical information and may lead to either no change or improved patient care. There are no risks to the patient as the patient will be receiving standard of care in both arms of the study. Patients will be critically ill requiring an emergency procedure and therefore, consent is not necessary for this study as per the criteria of the Common Rule for waiver of informed consent for emergency research.

Sample Size

A sample size calculation for this study is not possible as this is a pilot study and there is currently no reported data on the impact suctioning has on oxygen saturation during RSI in emergency department patients. For this reason we have decided to perform a convenience sample of 100 patients (50 in the judicious group and 50 in the continuous group). Data from this study will be used to provide statistics for a sample size and power calculation for a larger randomized control trial in the future.

Statistical Analysis

Descriptive statistics will be used for the cohorts. Means with 95% confidence intervals and medians with interquartile range will be used to describe the cohorts. Chi squared test will be used to compare the proportion of patients that experience desaturation between the cohorts. A simple student's t-test will be used to compare the mean oxygen saturations and end tidal oxygen levels measured between the cohorts.

Study Endpoints

The endpoint for this pilot study will be the enrollment of 50 patients in each group to a total of 100 patients.

References

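### SpO2 is recorded at the bedside by staff who can see the suction technique, with no monitor capture described, so lowest SpO2 and desaturation, and less so the primary SpO2, are open to arm-dependent recording error

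*Combined protocol and SAP*

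**What the plan says.** All places are in the combined protocol and SAP.

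- **Data Collection:** the section opens with "The data will be collected prospectively during the time of RSI by nursing and medical staff with the use of a data collection sheet". RPA staff are described as familiar with such sheets, Lincoln and Mount Sinai as collecting RSI data routinely, and staff at Maimonides and Mount Sinai as due to be trained in using the sheets.
- **Variables measured:** SpO2 and ETO2 are to be noted "at 10 second intervals starting with induction". The same list, which is said to be on the data sheet, includes the group: "Continuous versus judicious suctioning".
- **Intervention:** continuous suction is applied "throughout the procedure, including laryngoscopy and tube placement", whereas judicious suction is intermittent. Allocation is random once RSI has been decided on.
- **Outcomes:** "The primary outcome of this study is the oxygen saturation achieved (SpO_2) at the time of tube placement", with that moment fixed "via confirmation with first ETCO_2 waveform". Lowest saturation and desaturation incidence are secondary outcomes taken over the whole intubation period. ETO2 is a named outcome at two moments only, induction and ETT confirmation.
- **Statistical Analysis:** a t-test for mean saturations and ETO2 levels, and a chi-squared test for desaturation.

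The text describes no blinding, no independent or dedicated recorder, no monitor export or time-stamped capture, and no source check. Appendix 3 was not available, so any instructions printed on the sheet could not be read.

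**The concern.** The number on an oximeter is objective. Which displayed value is written down, to which second it is assigned, how it is rounded near the 90% cut-off, and whether a gap is filled from memory are not. When the person making those decisions can see the technique, they may go differently in the two groups, and the analysis cannot tell such a difference from an effect of suction.

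The exposure is uneven. Lowest SpO2 and desaturation depend on a complete series of readings taken during an emergency procedure, so one missed trough changes the outcome. The primary SpO2 is one value at a defined event. The recorder does not choose the moment freely, but the plan does not say how the first waveform is time-stamped or matched to a saturation reading.

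Error unrelated to group also has a cost here. The Sample Size section says the pilot will supply statistics for the design of a larger randomised trial, so mistimed or rounded values would distort the SD and event rates carried forward.

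**Working it through.** **The plan's own figure.** The only figure to check is the total: 50 + 50 = 100, which agrees. No alpha, SD, effect size or power is given, so what follows is illustration. The two-sided 5% level, the SDs, the shifts, the event rates and the procedure times are all assumptions.

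**Recording load.** Counting induction as time zero, a procedure of T seconds has T/10 + 1 time points.
- T = 60: 7 time points, 14 values (SpO2 and ETO2).
- T = 120: 13 time points, 26 values.
- T = 180: 19 time points, 38 values.

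**Mean SpO2.** With 50 per arm, SE = SD × √(2/50) = 0.2 × SD. If there is no true effect but recording shifts one arm by b points relative to the other, the false-positive rate is Φ(b/SE − 1.96) + Φ(−b/SE − 1.96), by normal approximation.

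| Assumed SD | SE | b = 0.5 | b = 1 | b = 2 |
|---|---|---|---|---|
| 5 | 1.0 | 7.9% | 17.0% | 51.6% |
| 10 | 2.0 | 5.7% | 7.9% | 17.0% |
| 15 | 3.0 | 5.3% | 6.3% | 10.2% |

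For example, at SD 10 and b = 1: Φ(0.5 − 1.96) + Φ(−0.5 − 1.96) = 0.072 + 0.007 = 7.9%.

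**What a shift would take for the event-anchored primary.** Assume 30% of patients are falling at 2 points per 10 seconds when the tube is confirmed. A systematic 10-second slip in one arm only moves the difference by 0.30 × 2 = 0.6 point, and a 20-second slip by 1.2 points. The false-positive rates are 9.2% and 22.4% at SD 5, and 6.0% and 9.2% at SD 10. On these assumptions a full 1-point shift needs 1/0.06 ≈ 17 seconds of one-sided slip. A slip of the same size in both arms would cancel if saturation is falling at a similar rate in each.

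**Desaturation.** Suppose the true rate p is the same in both arms and one arm misses 20% of its events. The observed difference is 0.20 × p. The chance of a significant result in that direction is Φ[(difference − 1.96 × SE₀)/SE₁], where SE₀ uses the pooled proportion and SE₁ the two separate proportions. The smaller opposite tail is ignored; with no misrecording this one tail would be 2.5%.
- p = 20%: observed 20% against 16%, 7.5%.
- p = 30%: observed 30% against 24%. SE₀ = √(2 × 0.27 × 0.73/50) = 0.0888 and SE₁ = √(0.30 × 0.70/50 + 0.24 × 0.76/50) = 0.0886, giving 9.9%.
- p = 40%: observed 40% against 32%, 12.9%.

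**ETO2.** The two named ETO2 outcomes are at induction and at ETT confirmation; at the second, an ETCO2 waveform is present. The 10-second ETO2 readings are a listed variable and not a named outcome, but the t-test sentence covers ETO2 levels without saying which.

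**The case against.** The strongest reply is that the primary outcome is a machine-displayed number tied to an observable event, and that staff are either used to recording these data or will be trained. This stands in part. The anchor limits the recorder's freedom, which is why the primary is the less exposed outcome. Familiarity and training may reduce careless error, but they do not hide the technique, and the secondary SpO2 outcomes have no such anchor.

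It can also be said that every shift above is assumed, must be systematic and one-sided to matter, and is modest for the primary at plausible slips. That is correct. A reader might infer from the table that the trial's result will be biased. The documents do not support this: they contain no evidence that differential error happens, in which direction, or by how much.

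A second tempting reading is that ETO2 readings are meaningless during apnoea and therefore compromise the SpO2 outcome. The documents do not support that either. They do not say when breathing stops, nor do they exclude breaths between attempts. They do not say how many people record, so distraction from SpO2 is conjecture. Whatever the 10-second ETO2 values mean, they are not the primary outcome and do not themselves bias SpO2.

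Finally, Appendix 3 may contain timing or print-out instructions that would answer part of the point.

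**Conclusion.** The concern holds as a gap in measurement safeguards. Recording is done at the bedside by staff who can see the technique, and the available text describes neither blinded reading nor monitor capture. That staff can see the group is an inference from the technique and the absence of any blinding, but a strong one. The exposure is greatest for lowest SpO2 and desaturation incidence, and smaller for the primary SpO2.

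The size is unknown. At 50 per arm, an assumed 1-point differential shift would raise a nominal 5% error rate to between 6.3% (SD 15) and 17.0% (SD 5). For the primary, plausible timing slips produce less than that. This is a worthwhile, inexpensive improvement to a pilot and not a flaw that invalidates it. The ETO2 question is separate and minor: it concerns which values are analysed.

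**What to change.** 1. In Data Collection, state that where a site's monitor stores SpO2 and capnography at adequate resolution, the primary SpO2, lowest SpO2, desaturation and the time of the first ETCO2 waveform are taken from the time-stamped export or print-out.
2. Have existing study staff read that record without the group shown.
3. Keep the data sheet as the fallback, record for each patient which source was used, and report the sources by group.
4. In Statistical Analysis, state that the ETO2 comparison uses only the values at induction and at ETT confirmation.

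The cost is a few sentences of wording, one export or print-out per patient, alignment of the monitor clock with the recorded event times, and a check at each site that storage is fine enough. The documents do not state storage resolution; a site that fails the check stays on the sheet and keeps the present exposure. Patient care is unchanged.

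### The primary comparison is an unadjusted t-test with no stated difference and confidence interval, although SpO2 before preoxygenation is collected; under true random allocation, omitting adjustment costs only precision

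*Combined protocol and SAP*

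**What the plan says.** The primary outcome is SpO2 at tube placement, confirmed by the first ETCO2 waveform (Primary Outcome). The Statistical Analysis section of the combined protocol and SAP gives one between-group method for it: a simple "t-test will be used to compare the mean oxygen saturations and end tidal oxygen levels measured between the cohorts". Confidence intervals appear only as description: "Means with 95% confidence intervals and medians with interquartile range will be used to describe the cohorts". No covariate is named, and neither is the population to be analysed.

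Under Variables measured, oxygen saturation and ETO2 are recorded "prior to starting preoxygenation and at induction (completion of preoxygenation". A secondary outcome counts falls of more than "10 points from baseline during the intubation period", without saying which reading is the baseline.

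The Sample Size section sets 50 patients per group with no power calculation, and gives the pilot's purpose: "Data from this study will be used to provide statistics for a sample size and power calculation" for a larger randomised trial.

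On timing and allocation, the Intervention section places enrolment after the choice of procedure ("Once the decision to perform RSI has been made by the treating team"), says "the patient will be enrolled into either a judicious or continuous suction group at random", and continues: "Rapid sequence intubation will then be performed in the standard means by the treating provider". The same section also leaves the manner of suctioning to the treating physician's judgement.

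**The concern.** A patient's saturation before preoxygenation may predict saturation at tube placement. Where it does, regression on that value gives a narrower interval for the same 100 patients. The value is already collected, yet the primary comparison ignores it.

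The pilot is also meant to feed a sample size calculation. What a planner wants from it is the estimated difference with its interval, the SD and, if the larger trial adjusts for baseline, the residual SD and r. The only between-group result that the plan commits to is a test. At stake are some precision and a clear statement of the planning quantities. The validity of the test is not in question if allocation is random.

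**Working it through.** **Inputs from the documents.** 50 per group, 100 in total (Sample Size); Student's t-test (Statistical Analysis); SpO2 before preoxygenation available (Variables measured).

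**Assumptions, because the documents give no figure.** Two-sided alpha 0.05; equal SDs, with results in SD units; r between 0 and 0.7; a 0.5 SD difference as an illustration for power. The plan has no calculated figure to reproduce.

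**Unadjusted analysis (98 df).** Half-width = t(0.975, 98) × √(2/50) = 1.984 × 0.2 = 0.397 SD. Power at 0.5 SD uses the noncentral t with noncentrality 0.5/0.2 = 2.5, which gives 69.7%.

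**Baseline-adjusted analysis (97 df).** The variance is multiplied by V = (1 − r²) × (1 + 1/96), where the second term allows for chance imbalance in the covariate. Half-width = t(0.975, 97) × 0.2 × √V, and the equivalent unadjusted total is 100/V. For r = 0.5, V = 0.75 × 1.0104 = 0.758, the half-width is 1.985 × 0.2 × 0.8705 = 0.346 SD and the equivalent total is 132.

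| Assumed r | Half-width (SD) | Power at 0.5 SD | Equivalent unadjusted total |
|---|---|---|---|
| unadjusted | 0.397 | 69.7% | 100 |
| 0 | 0.399 | 69.2% | 99 |
| 0.2 | 0.391 | 71.0% | 103 |
| 0.3 | 0.381 | 73.3% | 109 |
| 0.5 | 0.346 | 81.1% | 132 |
| 0.7 | 0.285 | 93.2% | 194 |

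Break-even is at r of about 0.10. On the SpO2 scale, with an assumed SD of 10 points, the half-width is 10 × 0.397 = 4.0 points unadjusted, 3.8 at r = 0.3 and 3.5 at r = 0.5.

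**Can the missing interval be recovered?** Each cohort's 95% CI has half-width 2.010/√50 = 0.284 SD, so the SD follows from it. With equal SDs, the half-width for the difference is √2 × 0.284 × (1.984/2.010) = 0.397 SD, the same figure as above. The unadjusted difference and its interval therefore follow from the planned summaries. The correlation r and the residual SD do not, but both can be computed from the patient-level data that the team will hold.

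**Does the ceiling at 100 matter?** A simulation of 20,000 trials used assumed inputs: latent baseline mean 94 and SD 6, latent outcome mean 94 and SD 7, both rounded and capped at 100. Type I error was 4.7–5.1% for the t-test and 4.7–5.2% for the adjusted analysis with robust (HC2) standard errors.

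**Does the condition on allocation matter?** In a second simulation with no true effect, the choice of group depended on baseline SpO2, with an assumed baseline gap of about 0.47 SD. The t-test was then biased by 0.14, 0.24 and 0.33 SD at r = 0.3, 0.5 and 0.7, with type I error of 11%, 22% and 38%. Adjustment held about 5% only because baseline SpO2 was the sole driver of choice in that simulation.

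**The case against.** The strongest reply is that the plan contains no error. Under random allocation the t-test is unbiased with the correct type I error, and a pilot with a convenience sample and no power target need not maximise power. This stands, and it is why the point is minor.

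The gain may also be close to nil. Preoxygenation lies between the two readings, so r may be low. At r of 0.2 to 0.3 the half-width shrinks by only about 1.5% to 4%. Nothing in the documents supports the r of 0.5 to 0.7 behind the larger gains, so the equivalents of 132 or 194 patients should not be read as a forecast. This stands too.

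Three stronger readings are tempting but unsupported:

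- A reader might infer that the planning statistics will be lost. They will not, because both SpO2 readings are collected for each patient, and no passage decides that the larger trial will adjust for baseline.
- A reader might infer that the cohort intervals will mislead, since they overlap until the difference reaches 2 × 0.284 = 0.568 SD while the interval for the difference excludes zero from 0.397 SD. But the t-test result will stand beside them.
- A reader might take the secondary outcome's baseline to be the reading before preoxygenation, and so conclude that the plan already treats it as such. The term is undefined and could equally mean the reading at induction.

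The objection does not remove the case for stating the difference with its interval. That is the natural result of a two-group comparison, and it serves the pilot's stated purpose at almost no cost.

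**Conclusion.** The concern holds as a minor point, for consideration. The plan names only an unadjusted test for its primary outcome, commits to no between-group difference with an interval, and leaves a collected baseline value unused. The missing interval is a gap in reporting. The missing adjustment costs precision, by an amount that the documents do not allow anyone to fix: negligible for r below about 0.2, small up to 0.3, and a narrowing of about 13% at r = 0.5.

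The conclusion that only precision is lost rests on two conditions: that allocation is truly random, and that patients are analysed as allocated. A reader might infer from the text that precision is the only possible loss in any case. The documents do not support that, because the Intervention section describes both random enrolment and physician discretion over suctioning, and no analysis population is given. A reader might equally infer that the t-test is biased and that baseline adjustment would repair it. The documents do not establish that discretion decides the group, and if it did, adjustment for one baseline value would not in general remove the confounding. The conflict over allocation is a separate matter and adds no weight to this point.

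**What to change.** Replace the sentence on the t-test for SpO2 in Statistical Analysis with wording such as:

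> The primary analysis is a linear regression of SpO2 at first ETCO2 waveform on randomised group, adjusted for SpO2 before preoxygenation, reporting the adjusted mean difference with its 95% CI (robust standard errors). The unadjusted mean difference with 95% CI (t-test) is a sensitivity analysis. The SD, residual SD and baseline-outcome correlation are reported for planning the larger trial.

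Robust standard errors are suggested because SpO2 is capped at 100.

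Use the reading before preoxygenation as the covariate, not the one at induction. The Intervention section counts the preoxygenation method among the aspects of RSI left to the clinician and places RSI after allocation, so the induction value could be affected by knowledge of the group.

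The plan does not say whether the reading before preoxygenation precedes allocation. If it cannot be taken as recorded before allocation is known, keep the unadjusted difference with its 95% CI as primary and the adjusted one as sensitivity.

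Separately, the statements in the Intervention section on random enrolment and on physician discretion must be reconciled.

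Cost: a paragraph of wording, with no new data or patients; one degree of freedom; and about half a point of power (69.7% to 69.2% at 0.5 SD) if r is near zero. Assuring the order of the baseline reading and allocation would be an operational step, which the fallback avoids.
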